**Table 1: Dosing Schedule**

No. of subjects	14
Dose of panitumumab-IRDye800	30 mg
Dose of Zr-panitumumab	1.0 mCi, allowable range 0.8 to 1.2 (29 to 44 Mbq)
Specific Activity of Zr-panitumumab	>200 Ci/mmol
PET imaging post-infusion*	Day 0 to the Day before Surgery
Timing of surgical procedure post-infusion	Day 2 to 5 post-infusion

Each subject will be followed for 30 days following the last dose of study medication.

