**Outcome measures to answer the primary and secondary objectives set:**

Preoperative data:

1. Collect safety data on tracer-infusion.
2. The number and location of F-FDG-PET positive nodes.
3. The number and location of Zr-panitumumab-PET positive nodes.

Intraoperative data:

4. The number and location of Zr-panitumumab-PET positive nodes.
5. The number and location of panitumumab-IRDye800 positive nodes.

Post-operative data:

6. Collect safety data in follow-up (up to 30 days post-infusion).
  - a. This includes tests and observations to identify both acute and late-treatment specific toxicity: vital signs; physical exam; toxicity grading; assignment of performance status; hematology; and blood chemistries (basic metabolic profile to include magnesium and phosphorus). NCI Common Toxicity Criteria v5.0 will be used for grading of toxicity.
7. Determine *ex vivo* fluorescence imaging information on panitumumab-IRDye800 (method described previously in (21)).
8. Determine the histo-pathological status of the primary tumor.
9. Determine the histo-pathological status of the lymph nodes: tumor-positive (isolated tumor cells, micro- or macro-metastasis) or tumor-negative.
10. Determine, using immunohistochemistry, on the surgically excised tissue specimens:
  - a. Tumor tissue viability
  - b. EGFR expression
  - c. Vessel density

We have previously described the methods for analysis in (26).

For qualification and quantification of the fluorescence signal and the radioactive signal, we follow the following rules:

- *Intraoperative fluorescence assessment of panitumumab-IRDye800:*

There will be no set level of fluorescence whereby we consider tissue positive or negative; it is based on operator's impression.

- *Ex vivo fluorescence assessment of panitumumab-IRDye800:*

From the fluorescence images taken in the operation room, we will calculate tumor-to-background ratios (TBRs) as such to define a more quantitative read-out (similar to as described in the IRB-35064 study). Based on the current data available from our IRB-35064, in our 50 mg cohort, we found an average TBR of  $6.53 \pm 1.2$ , a sensitivity of  $89 \pm 5.1\%$ , a specificity of  $92 \pm 3.5\%$  (AUC:  $0.93 \pm 0.05$ ). The NPV and PPV were  $94 \pm 2.8\%$  and  $92 \pm 9.5\%$ , respectively. We will extrapolate these findings to the current study to further validate the findings from our phase I study (IRB-35064).

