## **3. PARTICIPANT SELECTION AND ENROLLMENT PROCEDURES**

### **3.1 Inclusion Criteria**

1. Biopsy-confirmed diagnosis of squamous cell carcinoma of the head and neck.
2. Subjects diagnosed with any T stage, any subsite within the head and neck that are scheduled to undergo surgical resection. Subjects with recurrent disease or a new primary will be allowed.
3. Planned standard of care surgery with curative intent for squamous cell carcinoma.
4. Age  $\geq$  19 years.

5. Have acceptable hematologic status, coagulation status, kidney function, and liver function including the following clinical results:

Hemoglobin  $\geq$  9 gm/dL  
White blood cell count  $>$  3000/mm^3  
Platelet count  $\geq$  100,000/mm^3  
Serum creatinine  $\leq$  1.5 times upper reference range

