### **3.2 Exclusion Criteria**

1. Myocardial infarction (MI); cerebrovascular accident (CVA); uncontrolled congestive heart failure (CHF); significant liver disease; or unstable angina within 6 months prior to enrollment.
2. Previous bilateral neck dissection.
3. History of infusion reactions to monoclonal antibody therapies.
4. Pregnant or breastfeeding.
5. Magnesium or potassium lower than the normal institutional values.
6. Subjects receiving Class IA (quinidine, procainamide) or Class III (dofetilide, amiodarone, sotalol) antiarrhythmic agents.
7. Subjects with a history or evidence of interstitial pneumonitis or pulmonary fibrosis.
8. Severe renal disease or anuria.
9. Known hypersensitivity to deferoxamine or any of its components.

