**Table 5: Study Procedures**

	SCREENING/ PRE-TREATMENT (WITHIN 30 DAYS OF START OF TREATMENT)	DAY 0	DAY 1-4	DAY OF SURGERY (DAY 2 TO 5)	DAY 15 ( $\pm$ 4 days)	DAY 30 ( $\pm$ 4 days)
INFORMED CONSENT	X					
MEDICAL HISTORY	X					
PHYSICAL EXAMINATION 	X	X			X	
VITAL SIGNS	X	X		X	X	
HEIGHT AND WEIGHT	X					
PERFORMANCE STATUS 	X				X	
ECG	X 	X 			X	
CHEMISTRIES 	X	X		X	X	
HEMATOLOGY 	X				X	
TSH	X					
PTT/PT/INR	X					
SERUM PREGNANCY 	X	X				
PK-FLUORESCENT-LABELED ANTIBODY 		X	X	X	X	
PK-IMMUNOGENICITY 		X 			X	
IV INFUSION OF PANITUMUMAB-IRDYE800 		X				
BOLUS INJECTION OF  ZR-PANITUMUMAB 		X				
SURGICAL RESECTION 				X		
TUMOR IMAGING	X 	X 	X 	X 		
PATHOLOGICAL EVALUATIONS 				X		
ADVERSE EVENTS 		X		X	X	X
CONCURRENT MEDICATIONS 	X	X	X	X	X	X

1. A physical examination will be done at baseline; standard head and neck examination and system-oriented physical examination will be conducted on Day 0 and Day 15. Examinations do not have to be repeated on Day 0 if completed within 21 days prior to infusion. Performance status assessment will be done at baseline and Day 15. Examinations collected for surgical procedure are acceptable for screening purposes.
2. An ECG will be obtained at screening to evaluate baseline. A previous ECG that was obtained as part of standard of care may be used as the baseline ECG if obtained within 21 days prior to infusion.
3. On day of infusion, ECG will be collected 30 ( $\pm$ 10) min after the end of panitumumab-IRDye800 infusion. Also an ECG will be obtained at the end of the 1 hour ( $\pm$ 10 mins) observation period after completion of injection of Zr-panitumumab.

4. Chemistries to include a standard basic metabolic profile with magnesium and phosphorus. Chemistries and other blood work collected for surgical procedure are acceptable for screening purposes. Chemistries do not have to be repeated on Day 0 if completed within 21 days prior to infusion.
5. Hematology (i.e., CBC) values include WBC; RBC; Hgb; hematocrit and platelet counts. Blood work collected for surgical procedure are acceptable for screening purposes.

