6. A serum pregnancy test will be obtained on all women of childbearing age at baseline; a urine pregnancy test will be performed on Day 0 if the result of a serum pregnancy test within 72 hours before administration of panitumumab-IRDye800 is not available.
7. Blood samples for serum level of panitumumab-IRDye800 antibody and unconjugated dye, and  $^{89}\text{Zr}$ -panitumumab antibody will be drawn as follows: on Day 0 prior to panitumumab-IRDye800 infusion and at the end of the 1-hour ( $\pm 10$  mins) observation period after completion of injection of  $^{89}\text{Zr}$ -panitumumab; on Day 1-4 (only one sample will be collected on the same day when the PET/CT will be performed); on Day of surgery and on Day 15. The Day 15 time point will be 15 days  $\pm$  4 days, but is abbreviated as Day 15 throughout the protocol.
8. Blood will be collected on Day 0 prior to panitumumab-IRDye800 dose and on Day 15 and banked for future immunogenicity testing. Immunogenicity testing time points will not vary with dose.
9. Panitumumab-IRDye800 infusion to be given over 15 ( $\pm 5$  mins) minutes followed by 30 minutes ( $\pm 10$  mins) observation period.
10.  $^{89}\text{Zr}$ -panitumumab administered as a bolus injection to be done after the end of the observation period after panitumumab-IRDye800 infusion; will be followed by 1 hour ( $\pm 10$  mins) of observation period.
11. Surgical excision will be performed 2-5 days after the infusion of the study drugs.
12. A  $^{89}\text{Zr}$ -PET/CT scan will be acquired after injection of  $^{89}\text{Zr}$ -panitumumab. One scan will be performed at any time starting on Day 0 (after end of observation period post  $^{89}\text{Zr}$ -panitumumab administration) and until the day before surgery (inclusive). Subjects enrolled in the dosimetry sub-study will undergo three scans, performed at any time starting on Day 0 (after end of observation period post  $^{89}\text{Zr}$ -panitumumab administration) and until the day before surgery (inclusive); if available, the scans will be performed on Day 0, Day 1 and on the day before surgery.
13. A standard of care  $^{18}\text{F}$ -FDG-PET scan acquired within year from the day of study drug infusion is acceptable, even if this scan was/is acquired outside of Stanford.

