### 9.2.1 Screening/Pre-Treatment (Within 30 days of treatment start)

- Obtain written informed consent
- Medical history including current medications
- Assessment of performance status
- Physical examination
- Vital signs to include blood pressure, heart rate, respiratory rate, temperature
- Height and weight

- Basic metabolic panel, serum magnesium and phosphorus
- CBC (WBC, RBC, Hgb, hematocrit and platelet counts)
- TSH
- PT/PTT/INR
- Serum pregnancy test for women of childbearing potential
- ECG
- Assessment of concomitant medications.
- A standard of care F-FDG-PET scan acquired within a year from the day of study drug infusion is acceptable, even if this scan was/is acquired outside of Stanford.

*NOTE:* Labs and studies obtained for perioperative assessment can be used for screening evaluations.

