### **9.3.3 Medical History**

A complete medical history including age, sex, race, current medications, any current or previous medical conditions, any previous surgeries, smoking history, and alcohol use will be done at screening.

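### The FDG comparator scan may be up to a year old and no analysis by scan age is planned, so scan timing can distort the 89Zr–FDG comparison, in a net direction the documents do not settle

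*Combined protocol and SAP*

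**What the plan says.** Footnote 13 of Table 5 states that a standard-of-care FDG-PET "scan acquired within year from the day of study drug infusion is acceptable, even if this scan was/is acquired outside of Stanford". Section 9.2.1 repeats the rule: a "scan acquired within a year from the day of study drug infusion is acceptable". In Table 5 the FDG entry sits under "SCREENING/ PRE-TREATMENT (WITHIN 30 DAYS OF START OF TREATMENT", so the footnote is an express exception to that 30-day window. The synopsis and Section 2.4 add only that FDG imaging is standard of care and precedes enrollment.

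The 89Zr scan is placed at "Day 0 to the Day before Surgery" (Table 1), and surgery is on Day 2 to 5.

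Sections 10.1 and 12 score both tracers against histology from that one operation. Comparison with FDG on sensitivity and specificity belongs to the primary objective; comparison on false-negative odds and NPV belongs to the secondary objective. Section 12 has no FDG-to-surgery limit for these comparisons, no summary of scan age and no analysis that takes it into account.

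Three other provisions bear on the point:
- Section 3.1: "Subjects with recurrent disease or a new primary will be allowed".
- Section 3.2 excludes "Previous bilateral neck dissection". Neither section excludes earlier radiotherapy or systemic treatment.
- Section 2.4 grades nodes as "tumor-positive (isolated tumor cells, micro- or macro-metastasis) or tumor-negative".

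**The concern.** A paired comparison of two tests against one reference assumes that both tests looked at the same disease. Here one test is close to the reference and the other may be a year from it. A node that became metastatic in between is scored as an FDG miss, although FDG was never tested on it in that state. If 89Zr detects it, the node enters the comparison as a win for 89Zr. Since recurrent disease and new primaries are eligible, an accepted FDG scan can even predate the disease being staged.

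The stake is interpretation. If the report shows a sensitivity, false-negative or NPV difference between the tracers, nothing planned would tell a reader how much of it could be timing.

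**Working it through.** **1. The plan's own figure.** Inputs, all from the sample size paragraph of Section 12: 14 subjects, 30 nodes each, ICC 0.005, prevalence 7.5%, discordance 0.3, sensitivity difference 0.25, one-sided McNemar test at 0.05.
- Nodes: 14 × 30 = 420. Expected positive: 420 × 0.075 = 31.5.
- Design effect: 1 + 29 × 0.005 = 1.145. Effective nodes: 420 / 1.145 = 366.8 (plan: 367). Effective positive nodes: 366.8 × 0.075 = 27.5.
- Discordant cells: 0.275 and 0.025 (sum 0.3, difference 0.25). Exact one-sided power is 71.4% with 27 nodes and 73.6% with 28. The stated figure of more than 71% reproduces.

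**2. Timing.** FDG to surgery: at most 365 + 2 = 367 to 365 + 5 = 370 days. 89Zr to surgery: 1 to 5 days.

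**3. Late conversion.** Assume the tracers are equal when read at the same time. Let f be the share of positive nodes that converted after the FDG scan, Se_new the 89Zr sensitivity in those nodes, and p0 the rate at which they were already read FDG-positive. Other nodes contribute no difference, so

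spurious difference = f × (Se_new − p0).

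The documents give none of these inputs. Assumed ranges: Se_new 0.4 to 0.95, p0 0 to 0.05.

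| f | Positive nodes (of 31.5) | Spurious difference |
|---|---|---|
| 5% | 1.6 | 0.02 to 0.05 |
| 10% | 3.2 | 0.035 to 0.095 |
| 20% | 6.3 | 0.07 to 0.19 |

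For f = 10%: 0.10 × (0.4 − 0.05) = 0.035 and 0.10 × (0.95 − 0) = 0.095.

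To create the whole 0.25 design difference, f = 0.25 / (Se_new − p0). For Se_new 0.70 to 0.95 this is 0.25 / 0.95 = 26% to 0.25 / 0.65 = 38%. For Se_new 0.4 to 0.5 it is 0.25 / 0.5 = 50% to 0.25 / 0.35 = 71%.

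**4. Effect on the test.** Take true sensitivities of 0.70 for both tracers, discordance 0.15 each way, 28 positive nodes, and converted nodes invisible on FDG. The exact one-sided test then falsely favours 89Zr in 2.1% of trials at f = 0, 8.4% at f = 10% and 22.0% at f = 20%.

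**5. The opposite route.** Let g be the share of positive nodes that were imaged by FDG before treatment, partly responded, and still hold residual tumour at surgery. Let r be their FDG-positive rate on the old scan and Se_res the 89Zr sensitivity in the residual disease. They shift the difference toward FDG by g × (r − Se_res). The net shift is f(Se_new − p0) − g(r − Se_res). Its sign cannot be fixed without f and g.

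**6. Precision of a restricted comparison.** With m effective positive nodes kept out of n = 27.5 and a true difference of 0.25, the variance per node is 0.3 − 0.25² = 0.2375. The 95% half-width is 1.96 × √(0.2375/m). The chance SD of the restricted minus all-scans difference is √(0.2375 × (1/m − 1/n)). The trial enrols 7 cN0 and 7 cN+ subjects. Assume the cN+ cohort holds 80% to 100% of positive nodes.
- Two cN+ subjects left out: m = 27.5 × (1 − 2 × 0.8/7) = 21.2 to 27.5 × 5/7 = 19.6. Half-width 0.21 to 0.22; chance SD 0.051 to 0.059.
- Four left out: m = 14.9 to 11.8. Half-width 0.25 to 0.28; chance SD 0.086 to 0.107.

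Leaving out cN0 subjects would cost little. Nodes retained, not subjects retained, set the precision.

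**The case against.** The strongest case against acting has four parts.

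- **The direction is not one-way.** A reader might infer that an old FDG scan must favour 89Zr. The documents do not support that. Non-surgical treatment between the scans is not excluded, and residual micro-metastases count as positive, so a node seen by FDG before treatment can be missed by 89Zr afterwards. Nodes that both tracers miss add nothing to the sensitivity difference. For specificity the direction is open as well. This objection stands and is built into the conclusion.
- **Scans may well be recent.** One year is a cap. FDG imaging is standard of care, and pre-existing imaging informs cohort assignment. This is plausible, but nothing in the plan guarantees it or would show it in the report.
- **A restricted subset can differ in case mix.** If older scans belong mainly to recurrent or previously treated subjects, restricting by scan age also changes who is compared. This stands, and any difference must be reported with both explanations.
- **It is a pilot, and the subset will be imprecise.** This stands too. With two cN+ subjects left out, much of the 0.035 to 0.095 range lies within two chance SDs. The analysis can describe; it cannot settle the question.

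Previous bilateral neck dissection is excluded and nodes removed earlier are not in the specimen, which limits the role of earlier neck surgery. The 30-day heading and the one-year footnote are not a contradiction, since the footnote is an explicit exception.

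**Conclusion.** The concern holds as a gap in the analysis of the tracer comparison. The plan allows up to about a year between FDG and the reference histology, against at most 5 days for 89Zr, and plans nothing to show or examine the effect. Sensitivity, specificity, false-negative odds and NPV comparisons can all be distorted. Late conversion is the most direct route and favours 89Zr where 89Zr detects the nodes, but the net direction is not certain.

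The size is unknown. The 0.035 to 0.095 illustration rests on assumed values: equal tracers, 10% late conversion, Se_new 0.4 to 0.95 and p0 0 to 0.05.

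Two stronger readings should be set aside. One is that timing alone would readily produce the 0.25 design difference; that needs 26% to 38% of all positive nodes to convert late even with high 89Zr sensitivity in them. The other is that the sensitivity and specificity of 89Zr itself, or the outcome measure in Section 10.1 on positive nodes predicted by 89Zr, are compromised; neither uses the FDG scan. This is a cheap improvement, not a flaw that blocks the study.

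**What to change.** 1. Record and tabulate the FDG-to-surgery interval and any intervening neck or systemic treatment, overall and by cohort. Section 9.3.3 already covers "any current or previous medical conditions, any previous surgeries", but it does not name radiotherapy or systemic therapy, and the FDG scan is not an eligibility item in Appendix A. The fields should therefore be explicit.
2. Before the tracers are compared, prespecify a sensitivity analysis that repeats the 89Zr–FDG comparison in subjects whose FDG scan falls within an interval the investigators set and justify. List separately any scans that predate the current disease episode or the last treatment.
3. Report the estimate, 95% confidence interval and number of positive nodes beside the all-scans result. Judge precision by positive nodes retained.
4. Do not require significance to be kept. In simulation with a true 0.25 difference and no timing bias, a significant all-scans result lost significance in 13–19% of cases with 23–24 nodes kept, 31–37% with 19–20, and 65–71% with 13–14.
5. If the estimates differ, name scan timing and case mix as possible explanations and limit the comparative conclusion accordingly.

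Footnote 13 need not change, no scans are added, and no subject leaves the all-scans comparison or the 89Zr accuracy estimates. The cost is a few data fields, one extra analysis, an amendment with IRB approval (Section 11.1), and a subset result that is less precise and only descriptive.

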## 9.2 Study Procedures

Subjects screened and enrolled will follow schedule of evaluations provided at the beginning of this protocol. The following evaluations will be performed:

### 9.2.1 Screening/Pre-Treatment (Within 30 days of treatment start)

- Obtain written informed consent
- Medical history including current medications
- Assessment of performance status
- Physical examination
- Vital signs to include blood pressure, heart rate, respiratory rate, temperature
- Height and weight

- Basic metabolic panel, serum magnesium and phosphorus
- CBC (WBC, RBC, Hgb, hematocrit and platelet counts)
- TSH
- PT/PTT/INR
- Serum pregnancy test for women of childbearing potential
- ECG
- Assessment of concomitant medications.
- A standard of care F-FDG-PET scan acquired within a year from the day of study drug infusion is acceptable, even if this scan was/is acquired outside of Stanford.

*NOTE:* Labs and studies obtained for perioperative assessment can be used for screening evaluations.

### **9.2.2 Day 0**

- **Prior to Infusion**
  - Vital signs (blood pressure, heart rate, respiratory rate, temperature)
  - Assessment of performance status (within 21 days)
  - Physical examination (within 21 days)
  - Chemistries (electrolytes, creatinine, BUN, magnesium, phosphorus) (within 21 days)
  - Pregnancy test for women of childbearing potential. If the result of a serum pregnancy test within 72 hours before administration of panitumumab-IRDye800 is not available, a urine pregnancy test will be performed on Day 0
  - Blood sample for panitumumab-IRDye800 antibody and Zr-panitumumab antibody
  - Blood sample for future assessment of immunogenicity
- **IV infusion of panitumumab-IRDye800 over 15 minutes (± 5 mins)**
- **Vital signs immediately following panitumumab-IRDye800 infusion (+ 5 mins)**
- **Observation for 30 min (± 10 mins)**
- **ECG 30 min (± 10 mins) after the end of panitumumab-IRDye800 infusion**
- **Vital signs just before Zr-panitumumab administration**
- **IV injection of Zr-panitumumab bolus** followed by:
  - Vital signs immediately following Zr-panitumumab administration (+ 5mins)
  - Observation for 1 hour (± 10 mins)
  - Blood sample for panitumumab-IRDye800 antibody and Zr-panitumumab antibody collected at 1 hour (± 15 mins) after administration of Zr-panitumumab
  - ECG will be obtained at 1 hour (± 15 mins) after administration of Zr-panitumumab
  - Assessment for adverse events at the end of the 1 hour observation period
- **DOSIMETRY STUDY ONLY:**
  - Zr-panitumumab whole body PET/CT imaging after completion of observation

### **9.2.3 Day 1 to Day before Surgery:**

- The following assessments will be performed once, at any time between Day 1 and the day before surgery (including on Day 1 and on the day before surgery):
  - Blood sample for panitumumab-IRDye800 antibody and Zr-panitumumab antibody.
  - Zr-panitumumab whole body PET/CT imaging.

- Assessment for adverse events.
- Assessment for concomitant medications.
- Imaging using the optical and radiotracer imaging/detection devices in the clinic to assess fluorescence and radiotracer intensity if tumor amenable to imaging and depending on subject availability.
- DOSIMETRY STUDY ONLY:
  - A total of two Zr-panitumumab whole body PET/CT scans will be performed at any time between Day 1 and the day before surgery (including on Day 1 and on the day before surgery if possible); if available, the scans will preferably be performed on Day 1 and on the day before surgery.
  - Blood sample for panitumumab-IRDye800 antibody and Zr-panitumumab antibody will be collected on the same days when PET/CT imaging is performed.

#### **9.2.4. Day 2 to 5 (Day of Surgery)**

- Prior to surgery: Vital signs (blood pressure, heart rate, respiratory rate, temperature)
- Chemistries (electrolytes, creatinine, BUN, magnesium, phosphorus)
- Blood sample for panitumumab-IRDye800 antibody and Zr-panitumumab antibody
- Scheduled routine surgical resection, per standard of care
- Intraoperative imaging using the optical and radiotracer imaging/detection devices (if accessible for imaging; Appendix B and C)
- Pathological evaluations – tissue assessments of the pathological tissues by optical scanning after clinical assessment by pathologist but prior to permanent fixation of the tissue
- Assessment for adverse events
- Assessment for concomitant medications

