## **2.4 Study Design**

### **For clinicaltrials.gov and Stanford Clinical Trials Directory compliance:**

- The primary purpose for the protocol is to develop a universal lymph node detection strategy. This study evaluates if systemic injections of Zr-panitumumab in conjunction with panitumumab-IRDye800 can be used to identify tumor-loaded lymph nodes to expand the capabilities of non-invasive and intraoperative cancer imaging.
- The interventional model is **Sequential**.
- There are **2 cohorts**. Both cohorts will receive the same treatment
- The study is **open-label**. No masking is used.
- The study is **non-randomized**.
- The primary outcome is **the number (proportion) of lymph nodes determined to be tumor-positive by histological and/or pathological evaluation that were predicted to be tumor-positive by Zr-panitumumab PET/CT imaging**.
- The secondary outcome is **the number (proportion) of lymph nodes determined to be tumor-positive by histological and/or pathological evaluation that were NOT predicted tumor-positive by Zr-panitumumab PET/CT imaging**.

The study is an open-label pilot study to determine the efficacy of Zr-panitumumab in tumor-loaded node detection in subjects with HNSCC that undergo surgery with curative intent. It is anticipated that 14 subjects will be enrolled into the study. Subjects will be enrolled to the node negative (no suspicion of tumor-positive lymph nodes in the neck; cN0) or node positive (suspicion of tumor-positive lymph

nodes in the neck; cN+) group based on the preoperative work-up, which includes a physical exam and evaluation of the pre-existing imaging data.

All subjects will receive a dose of 30 mg panitumumab-IRDye800. Subjects will subsequently receive 1 mCi +/- 20% of Zr-panitumumab. If at any point after infusion, 2 subjects experience a DLT (Grade 2 or greater toxicity), then the study will stop, and safety data will be reviewed.

The known rate of infusion reactions of panitumumab is 1% (package insert); therefore, we expect a DLT rate of approximately 1% or higher with panitumumab-IRDye800 or Zr-panitumumab. The probability of observing two or more DLTs within a 10-subject cohort (requiring stopping the study) is 0.4%; if the DLT rate is as high as 5%, the probability of 2 or more DLT is 8.6%.

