For an overview of the proposed study, see Study Schema (page 9), and the dosing schedule below. Briefly, subjects will undergo F-FDG-PET prior to study enrollment, as is standard of care. Administration of panitumumab-IRDye800 will occur by IV over 15 minutes, followed by a 30-minute observation period. Administration of Zr-panitumumab will occur by IV, per radioactive drugs administration policies. The subjects will be observed for 1 hour following the Zr-panitumumab injection.

After infusion of study agents on Day 0, subjects will undergo Zr-panitumumab PET/CT imaging. One scan will be performed at any time starting on Day 0 (after end of observation period post Zr-panitumumab administration) and until the day before surgery (inclusive). Subjects enrolled in the dosimetry sub-study will undergo three scans, performed at any time starting on Day 0 (after end of observation period post Zr-panitumumab administration) and until the day before surgery. If available, the scans will be performed on Day 0, Day 1 and on the day before surgery.

Subjects will undergo surgical resection 2-5 days after infusion of study drugs. Imaging will be performed intraoperatively using a novel beta probe and/or high-energy gamma probe (see Appendix C for a list of devices) and the optical imaging devices (see Appendix B for a list of devices), to assess the tumor and lymph node(s) prior to resection, and the wound bed after surgical removal. The surgery will be conducted in the standard of care, and the surgeon will not use the imaging data to make decisions.

*Ex vivo*, imaging of the specimens prior to pathological assessment will be performed using non-invasive imaging modalities that do not violate or destroy the tissue. These may include beta probe and/or high-energy gamma probe, an open-field imaging system, a closed-field imaging system and a fluorescence flatbed scanning device (see Appendix B and C for a list of devices). Additionally, a closed Cherenkov imaging system may be used to image the specimen after removal (see Appendix C). Methods have been described in detail in the literature (20-25).

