### **Exploratory Objectives**

- **Determine the sensitivity and specificity of panitumumab-IRDye800 for the detection of tumor-involved regional lymph nodes.**
- After isolation of lymph nodes from the specimen in the pathology lab, lymph node fluorescence will be measured prior to histological and/or pathological evaluation (gold standard). Sensitivity and specificity will be generated by comparison of fluorescence intensity and histological and/or pathological evaluation (gold standard). Findings will furthermore be compared to the sensitivity and specificity of Zr-panitumumab and F-FDG (primary objective) using Durkalski's test, as outlined above.

- Determine the number (proportion) of lymph nodes determined to be tumor-positive by histological and/or pathological evaluation that were NOT predicted tumor-positive by panitumumab-IRDye800 labeling.
- We will determine the level of association between panitumumab-IRDye800 results and  $^{89}\text{Zr}$ -panitumumab-PET and  $^{18}\text{F}$ -FDG-PET results with the Phi coefficient.

Descriptive statistics

For qualification and quantification of the fluorescence signal and the radioactive signal, we follow the following rules:

- *Intraoperative fluorescence assessment of panitumumab-IRDye800:*  
There will be no set level of fluorescence whereby we consider tissue positive or negative; it is based on operator's impression.
- *Ex vivo fluorescence assessment of panitumumab-IRDye800:*  
From the fluorescence images taken in the operation room, we will calculate tumor-to-background ratios (TBRs) as such to define a more quantitative read-out (similar to as described in the IRB-35064 study). Based on the current data available from our IRB-35064, in our 50 mg cohort, we found an average TBR of  $6.53 \pm 1.2$ , a sensitivity of  $89 \pm 5.1\%$ , a specificity of  $92 \pm 3.5\%$  (AUC:  $0.93 \pm 0.05$ ). The NPV and PPV were  $94 \pm 2.8\%$  and  $92 \pm 9.5\%$ , respectively. We will extrapolate these findings to the current study to further validate the findings from our phase I study (IRB-35064).
- *Radioactive assessment of  $^{89}\text{Zr}$ -panitumumab:*  

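### Section 9.2.4 scans tissue after the pathologist's clinical assessment, while Section 2.4 and the synopsis image it before, so the exploratory dye call could be made knowing the pathologist's impression

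*Combined protocol and SAP*

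**What the plan says.** The plan places fluorescence measurement of excised tissue at several points.

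- **Section 2.4, Study Design:** "imaging of the specimens prior to pathological assessment will be performed using non-invasive imaging modalities". The devices it lists include open-field, closed-field and flatbed fluorescence systems. The Treatment Schedule row of the synopsis gives the same order.
- **Sections 1.3 and 12, exploratory objectives:** once the nodes have been separated out in the pathology laboratory, "lymph node fluorescence will be measured prior to histological and/or pathological evaluation (gold standard").
- **Section 9.2.4, day of surgery:** tissue is assessed by "optical scanning after clinical assessment by pathologist but prior to permanent fixation of the tissue".

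On how the signal becomes a result, Section 12 (repeating 2.4) has two rules. For the intraoperative read: "There will be no set level of fluorescence whereby we consider tissue positive or negative; it is based on operator's impression". For the ex vivo read: "From the fluorescence images taken in the operation room, we will calculate tumor-to-background ratios (TBRs) as such to define a more quantitative read-out". No threshold on that ratio is given. The design list in 2.4 states "No masking is used". No section describes masking of the person who reads the fluorescence.

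Section 12 compares dye sensitivity and specificity with 89Zr-PET and FDG-PET by Durkalski's test, and applies the 0.05 level to exploratory as well as primary analyses.

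**The concern.** In an accuracy study, the index test should be read without knowledge of the reference assessor's view of the same tissue. Staff who follow 9.2.4 would scan after the pathologist has already looked. If that scan decides whether a node counts as dye-positive, the reader may know which nodes appeared to contain tumor. With no fixed cutoff, a faint signal in a suspicious node could be accepted and the same signal in an unremarkable node dismissed. Apparent sensitivity and specificity of the dye could then be too high.

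The comparisons with PET would be tilted as well. Section 10.1 has both PET reads made before surgery, so neither can borrow from the pathologist. Exploratory results are intended for publication (Section 1.3), so a tilt here could reach readers as evidence that the dye outperforms PET at node level.

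**Working it through.** The plan states no figure on this point, so the check is mainly a comparison of text.

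| Place | What is imaged | After | Before |
|---|---|---|---|
| Synopsis; Section 2.4 | Excised specimen, several devices | Resection | Pathological assessment |
| Sections 1.3 and 12 | Individual nodes | Isolation in the pathology laboratory | Gold-standard evaluation |
| Section 9.2.4 | Pathological tissues, optical scan | Pathologist's clinical assessment | Permanent fixation |
| Sections 2.4 and 12, ex vivo ratio | Operating-room images | Not stated | Not stated |

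1. **Section 2.4 and the synopsis against 9.2.4.** One order is imaging then assessment, the other is assessment then scanning. Section 2.4 says pathological assessment without limiting it to histology, and names scanning devices. On a plain reading the two conflict.

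2. **Sections 1.3 and 12 against 9.2.4.** Section 10.1 identifies histology as the gold standard. The sequence clinical look, node isolation, scan, fixation, histology satisfies all three sections. There is no necessary conflict.

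3. **Which scan supplies the node result.** There are three candidates: operating-room images (ex vivo ratio, Section 12), fluorescence of isolated nodes (Sections 1.3 and 12), and the optical scan in 9.2.4. Appendix B separates in vivo, back-table and laboratory devices but does not link any of them to the node-level call. The documents leave this open.

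4. **What protects the reading.** For 89Zr-PET there is a tentative cutoff of 1.4 times the mediastinal background. For ex vivo fluorescence there is none, although excised tissues are to be scored yes or no. Reader masking is not mentioned.

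5. **What is exposed.** Dye sensitivity and specificity, the proportion of positive nodes the dye misses, and the dye-versus-PET comparisons all use the dye call. The 89Zr-versus-FDG sensitivity, specificity, false-negative odds and negative predictive value do not.

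6. **Scale per node.** Section 12 plans 14 × 30 = 420 nodes at 7.5% prevalence. That is 420 × 0.075 = 31.5 positive nodes and 420 − 31.5 = 388.5 negative nodes. One changed call moves apparent sensitivity by 1/31.5 = 3.2 percentage points, or apparent specificity by 1/388.5 = 0.26 points. How many calls would change is not given and cannot be derived, so this is a conversion rate and not an estimate of bias.

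**The case against.** The strongest reply is that these are different steps. Back-table imaging comes first, and the scan in 9.2.4 is a later laboratory step that need not decide anything. Tissue is still unfixed at that scan, so final histology is unknown. Positive nodes include isolated tumor cells and micro-metastases (Section 2.4), which a first look would not be expected to show. The ex vivo read-out is image-derived and not an impression. Dye accuracy is only exploratory.

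Much of this stands, and it rules out several stronger readings that a reader might infer:

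- **That 1.3 and 12 contradict 9.2.4.** They do not if the gold standard is final histology. Some handling before measurement is built into them, since nodes must first be isolated in the pathology laboratory.
- **That the dye call is made after the pathologist's inspection.** No section says the 9.2.4 scan supplies the call.
- **That the operator's impression decides the ex vivo result.** That rule covers the intraoperative read only.
- **That the no-masking statement means readers will know the pathologist's view.** It sits in a registry list beside open-label and non-randomized and describes the trial design. On reader masking the documents are silent.
- **That accuracy will rise by a stated amount.** The documents give no basis for the share of errors a gross impression would correct.

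What the reply does not remove is the conflict of order. Section 2.4 itself lists closed-field and flatbed scanning among the imaging done before pathological assessment, so separating back-table from laboratory steps does not fully reconcile it with 9.2.4. Nor does the reply say which measurement counts.

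**Conclusion.** The concern holds as a conflict in measurement order with an open route to bias. Section 9.2.4 disagrees with Section 2.4 and the synopsis. Because no ex vivo cutoff, no reader masking and no designated scan are given, following 9.2.4 permits the dye call to be made with the pathologist's impression known. Any resulting bias would probably favour the dye, both in its own accuracy estimates and against the two preoperative PET reads.

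This rests on two assumptions: that clinical assessment in 9.2.4 means something like gross inspection, and that the resulting impression can reach the person scoring fluorescence. The size is not estimable from the documents. The effect is confined to analyses that use the dye result; the primary 89Zr-versus-FDG comparison does not. The correction is worth making because it is cheap and Section 2.4 already implies it.

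**What to change.** 1. Reconcile 9.2.4 with Section 2.4 and the synopsis so that one order of imaging and pathological assessment is stated throughout.
2. Name the scan that supplies the node-level dye result.
3. Record and lock each node's fluorescence value and its positive or negative call before the reader knows the pathologist's impression.
4. Where isolating nodes in the pathology laboratory means the pathologist sees them first, have the existing reader score the images without being told that impression. Flag those nodes on the CRF and repeat the dye accuracy analysis without them.

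The cost is a few sentences of protocol text, one CRF field and one small sensitivity analysis. No extra scan and no additional reader are needed.
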